We will quantify overground walking ability using the 10MWT.⁴⁹ Subjects will perform 2 trials each of the 10MWT at their fastest but safe speed with a minimum of 1-minute rest between trials. Average speed across the two 10MWT trials will be used for analyses. The validated assessment tool will provide an indication of return of our subject population to pre-morbid activities following the initial neurological insult. The 10MWT has high inter-rater reliability, and the rating procedure can be accomplished in approximately 30 minutes.

The screening and physical assessment procedures will last approximately 1.5 hours.

To ensure safety, we also will assess pain, spasticity, systemic hypertension, and autonomic dysreflexia prior to and following caffeine and AIH interventions. We routinely measure pain, spasticity, and incidence of hypertension and autonomic dysreflexia as part of our study protocols in persons with chronic SCI.^{32, 33} We will make measurements at baseline, after session 5, and one-week follow-up, and again at two-weeks follow-ups.

Quantify pain: We will assess pain severity using the Wong-Baker FACES scale of 0 (no pain) to 5 (extreme pain).^{59, 60}

DETAILED STUDY PROTOCOL

Quantify spasticity: We will assess spasticity using the Spinal Cord Assessment Tool for Spastic Reflexes (SCATS).⁵⁸ We will quantify total lower extremity spasticity score using the cumulative sum of 3 SCATS subscales: clonus (0=no spasticity; 3=severe), flexor (0=no spasticity; 3=severe), and extensor (0=no spasticity; 3=severe).

Quantify systemic hypertension incidence rate: In addition to monitoring during the intervention, we will measure systolic and diastolic BP at baseline, after sessions 5, and again at follow-ups. We will define a systemic hypertensive event as a systolic pressure exceeding 140 mmHg and/or diastolic pressure exceeding 90 mmHg.^{46, 47}

We will compute hypertension incident rate for each intervention group as the number of hypertensive events divided by the total person-time. We define person-time in units of person-measures (the sum of the total number of BP measurements) taken for each person. Person-measures accounts for the total number of chances for detecting a hypertensive event and accounts for measurements not made due to drop-out or a disqualifying adverse event.⁶³ Finally, we will compute Relative Risk for each Aim as the incidence rate in the dAIH groups over the incidence rate in the dSHAM groups.⁶⁴

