Quantify autonomic dysreflexia incidence rate: We will assess the occurrence of autonomic dysreflexia in all intervention groups. Systolic blood pressure (SBP) will be measured as detailed in common methods. We will assess SBP at baseline, and before, during and immediately after breathing interventions, and again at follow-ups. Additional SBP measurements will be made if participants first present with symptoms characteristic of autonomic dysreflexia (e.g., headache, diaphoresis, blurred vision). An autonomic dysreflexia event will constitute a participant having a SBP increase from baseline of 20 mmHg or SBP greater than 150 mmHg with complaints of headache, diaphoresis, and/or blurred vision and will be diagnosed by our study team clinicians (physicians and physical therapists). An autonomic dysreflexia event will result in termination of study participation and require prompt evaluation by the team physicians and emergency medical team.

We will compute autonomic dysreflexia incident rate for each group as the number of autonomic dysreflexia events divided by the total person-time. We define person-time in units of person-days (the number of days a person remains in the study). Person-days accounts for the total number of chances for detecting autonomic dysreflexia and accounts for days on which measurements were not made due to drop-out or a disqualifying adverse event.⁶³ Finally, we will compute Relative Risk as the ratio of incidence rates between groups.⁶⁴

We previously demonstrated that daily exposures of AIH (up to 5 consecutive days) do not elicit adverse clinical events in persons with chronic SCI.^{32, 33} Similarly, rodents exposed to daily exposure for 7 consecutive days did not induce hippocampal cell death, changes in body mass, or hypertension,^{8, 9} including in animals early after injury.⁸ Determining whether dAIH or in combination protocols lead to the onset of significant pathology (pain, spasms, hypertension, autonomic dysreflexia) in persons with SCI is essential for establishing safe delivery of caffeine combined with AIH in this earlier stage of injury.

Quantify inflammation: We will quantify inflammation using measures of C-reactive protein concentrations in the blood.

- Participant retention plans: Whether or not you complete the whole study, we will pay you \$25 for each visit you do complete. We will also reimburse for up to \$100 per visit in travel

DETAILED STUDY PROTOCOL

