• Blinding Questionnaire		x	x	x	x	x			
• Weight (kg)	x						x	x	
Safety Outcomes									
• Pain (0-10)	x	x	x	x	x	x	x	x	
• Blood pressure (mmHg)	x	x	x	x	x	x	x	x	
• Heart rate (BPM)	x	x	x	x	x	x	x	x	
• Oxygen saturation (%)	x	x	x	x	x	x	x	x	
• Memory (0-30)	x	x	x	x	x	x	x	x	
Biomarkers									
• CYP1A2 Polymorphism	x								
• Caffeine serum level (mg/L)		x				x			
• Inflammation (CRP)		x			x		x		

IV. Statistical Principles

We plan to use a parametric linear mixed model since this method is sensitive to within subject changes and robust against variability, small sample sizes, and missing/unbalanced data sets as compared to other statistical models.²⁶ If the results do not meet these model assumptions, we will apply alternative non-parametric tests.

16. Level of significance

All applicable statistical tests will be 2-sided and will be performed using a 5% significance level.

17. Adjustment for multiplicity

we do not plan to adjust for multiplicity.

18. Confidence intervals

Statistical comparisons will include 95% (2-sided) confidence intervals (CIs).

19. Adherence and protocol deviations

We will record a deviation (if the even does not significantly affect a participant's rights, safety, or well-being, or trial outcomes), or a violation (if the deviation may potentially significantly impact the completeness, accuracy, and/or reliability of the trial data or that may significantly affect a patient's rights, safety, or well-being). All protocol deviations/violations will be logged, but no formal statistical testing will be performed.

Adverse events will be reported on an IRB-approved electronic Case Report Form (eCRF). Details will include the type of event, date of onset, duration, intensity, causality relationship to the study drug(s), and outcome. If an adverse event should occur, every attempt will be made to obtain as much information as possible about event evaluation and outcome. If a serious adverse event occurs, the treatment will be interrupted or discontinued at the physician investigator's discretion. All protocol deviations will be reported to the PI ([name]) and the IRB.

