Alternative statistical methods: If distributions are not normal, we will perform comparable nonparametric tests. If baseline measures are significantly different between sessions (interventions), an analysis of co-variance (ANCOVA) will be used to analyze the data.

Blinding integrity analysis: we plan to rigorously quantify blinding integrity here. We will ask participants and raters to guess the intervention received at the end of each intervention and indicate guess confidence using a Likert scale.^{38,39} We will use a contingency table and Fischer's Exact Test to determine if the probability of correct guessing is different from chance. Using multivariate logistic regressions, we also will assess factors that may influence guessing (i.e., adverse events, perceived effects, and sensorimotor changes). In the event of a medical emergency, we will unblind the PI, study participants, and care provider. We also will notify IRB of treatment allocation during adverse event reporting as necessary.

CYP1A2 analysis: we will perform subgroup analysis on our study cohort to determine the extent to which differences in caffeine metabolism due to CYP1A2 polymorphisms may affect responsiveness to the combinatorial treatment of caffeine+AIH.

28. Missing data

Rigorous efforts will be made to ensure complete outcome data. However, we anticipate that participants in this study cohort may be unable to complete the study requirements. Missing data will be reported and documented as we did in our previous clinical trial.⁴⁰ We will document reasons for missing data and our approach to handle missing data during statistical analysis. We will account for potential outliers in our results using a conservative outlier labeling technique set forth by Hoaglin and Tukey.⁴¹

29. Additional analyses

We do not anticipate any additional statistical analyses methods.

30. Harms

Checklists and note pages are used to log any deviations or omissions from the protocols. Any clinical/health related issues would be immediately presented to the subject to determine appropriate notification (i.e., current physician or appropriate specialist). Based on the seriousness of the situation Drs. [name] or [name] may be contacted to provide clinical guidance on the appropriate course of action as per our Laboratory Medical Emergency Safety Plan.

31. Statistical software

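### An autonomic dysreflexia event ends study participation, not only treatment, so that round's remaining walking, blood pressure and pain assessments are lost

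*Combined protocol and SAP*

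**What the plan says.** **The rule.** Protocol 18, in the part on autonomic dysreflexia incidence: "An autonomic dysreflexia event will result in termination of study participation", with prompt evaluation by the physicians and the emergency team.

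**When an event can be found.** The same part of Protocol 18: "We will assess SBP at baseline, and before, during and immediately after breathing interventions, and again at follow-ups".

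**What is scheduled.** For the safety measures, Protocol 18 says: "We will make measurements at baseline, after session 5, and one-week follow-up, and again at two-weeks follow-ups". Table 1 also marks blood pressure and pain on each of the five treatment days. The primary outcome, 10MWT, is analysed at BL, D5, F1 and F2 (Protocol 20, SAP 26 and 27).

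**How the rates allow for lost data.** The dysreflexia rate uses person-days, which are meant to allow for "days on which measurements were not made due to drop-out or a disqualifying adverse event". The hypertension rate uses person-measures, a denominator that "accounts for measurements not made due to drop-out or a disqualifying adverse event".

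**Other adverse effects.** Protocol 11b and SAP 13 stop the interventions or the treatment. They do not say that participation ends.

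**Missing data.** SAP 28: "we anticipate that participants in this study cohort may be unable to complete the study requirements". It promises to document the reasons and the handling. SAP IV describes the mixed model as "robust against variability, small sample sizes, and missing/unbalanced data sets". On adverse events, SAP 19 says "every attempt will be made to obtain as much information as possible about event evaluation and outcome".

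**The concern.** Stopping caffeine and hypoxia after dysreflexia is plainly right. Stopping the assessments is a separate decision, and the rule takes both at once. A dysreflexia event during a round could be caused by caffeine, by hypoxia or by both. Whether the later values of that round are missing may therefore depend on the intervention received. A mixed model can be fitted with visits missing, but it does not remove that dependence.

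On the safety side, Protocol 18 calls it essential to find out whether these combinations bring on pain, hypertension or dysreflexia. The rule ends scheduled blood pressure and pain readings in the very participants who had such an event. The readings that would show, on the trial's own timetable, whether the effect had settled are not taken.

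**Working it through.** The plan gives no figure to reproduce here: no event rate and no expected loss from this rule. The check is a reading of the text and a count of visits.

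**Step 1: does any other text restore the visits?**

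- The person-days definition is part of the dysreflexia text and expects days without measurement after a disqualifying event. This agrees with the literal reading of the rule. The person-measures wording is generic and belongs to the hypertension rate, so it is consistent but weaker support.
- The SPIRIT checklist (item 18b) points to the protocol for the outcome data to be collected from people who discontinue. The retention plan in Protocol 18 covers only payment, travel and lodging.
- SAP 19 follows up the event itself, not the D5, F1 and F2 outcomes. SAP 24 and SAP 28 document losses and reasons.
- Protocol 12 mentions 10MWT at the end of each training session. Such values do not substitute, because SAP 26 restricts all analyses to BL, D5, F1 and F2.

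Nothing restores them.

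**Step 2: 10MWT visits lost.** Inputs: 3 rounds, each with 3 post-baseline walks (D5, F1, F2), so 3 × 3 = 9 per participant. Within a round, systolic pressure is checked at 5 sessions + 2 follow-ups = 7 visits after baseline. The D5 assessment follows session 5, so an event in any of the 5 sessions precedes it.

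Let r be the round of the event and v the number of that round's post-baseline walks not yet done.

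- As written: lost = v + 3 × (3 − r).
- With the interventions stopped but visits kept: lost = (v − k) + 3 × (3 − r), where k, from 0 to v, is the number of walks medically permitted and consented to.

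| Event | v | Lost as written (r = 1 / 2 / 3) | Lost with the change (r = 1 / 2 / 3) |
|---|---|---|---|
| Any of sessions 1–5 | 3 | 9 / 6 / 3 | 6–9 / 3–6 / 0–3 |
| F1, before the walk | 2 | 8 / 5 / 2 | 6–8 / 3–5 / 0–2 |
| F1, after the walk | 1 | 7 / 4 / 1 | 6–7 / 3–4 / 0–1 |
| F2, before the walk | 1 | 7 / 4 / 1 | 6–7 / 3–4 / 0–1 |
| F2, after the walk | 0 | 6 / 3 / 0 | 6 / 3 / 0 |

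The term 3 × (3 − r) is the later rounds. They are lost either way, because no further treatment should be given.

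One event in a session removes 1/20 = 5% of the planned participants from that intervention at all three analysed time points.

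**Step 3: blood pressure and pain.** For an event in sessions 1–4, the D5, F1 and F2 readings are still due and are lost. For an event in session 5, some D5 blood pressure already exists, because pressure is taken around and during the session (Protocol 11a, Protocol 18, Table 1). The loss is then any D5 reading still due, plus F1 and F2.

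**The case against.** **Withdrawal is a deliberate safety rule.** Safety requires that caffeine and hypoxia stop, and they would. Blood pressure and pain checks are not the hazard. For 10MWT, performed at the fastest safe speed, the objection has force, so walks should depend on medical permission.

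**Kept walks may be unblinded.** Protocol 20 and SAP 27 unblind the participant, the care provider and the investigator in a medical emergency, and Protocol 18 sends every dysreflexia event to the emergency team. 10MWT depends on effort, so a participant who knows the allocation may walk differently. This stands. It is a reason to record unblinding and to analyse with and without these walks, and no reason to stop the safety readings.

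**Kept walks may follow a partly delivered round.** An event in session k means at most k of 5 sessions were given, while the stated aim concerns five consecutive days. This also stands. Such values estimate the effect of the assigned intervention, not of the full course.

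**Most of the loss cannot be recovered.** True for early events. For a round-1 event, 6 of the 9 lost walks belong to later rounds, and the participant has no paired caffeine+AIH versus placebo+AIH difference either way.

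**Attrition is already planned for.** The sample size includes 17% attrition, 0.17 × 20 = 3.4 participants. That protects power. It does not address missingness related to treatment.

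**Events will be rare.** Probably. Protocol 10 excludes severe dysreflexia, hypertension and cardiovascular disease, and Protocol 11b excludes any history of dysreflexia. This limits the size of the problem but does not change the rule.

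**Conclusion.** The point holds and is minor. As written, dysreflexia in a session ends that round's D5, F1 and F2 walks and the blood pressure and pain readings still due, in participants whose event may be related to the intervention. The conclusion rests on the literal wording of Protocol 18 and on the absence of any other provision for those visits. It assumes no event rate and no size of bias. The documents give neither, and the exclusions suggest that events will be uncommon. The clearer gain from a change is in safety follow-up; the gain for the primary outcome is less certain.

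A reader might infer more than the documents support:

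- *That the event itself drops out of the safety analysis.* It does not. It counts in the incidence rate and is followed under SAP 19.
- *That all D5 blood pressure is lost.* Not for a session-5 event.
- *That keeping the visits recovers three walks per event.* Three is the maximum for a session event; the range is 0 to 3.
- *That the same loss occurs under Protocol 11b and SAP 13.* Those sections stop interventions only and do not cancel visits, so no loss is shown there.
- *That the primary comparison is materially biased.* Nothing in the documents allows that to be estimated.

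**What to change.** **Protocol 18.** Replace the end of study participation with permanent discontinuation of the study interventions, with no further rounds. Keep that round's remaining D5, F1 and F2 visits unless consent is withdrawn: blood pressure and pain in all cases, 10MWT only where medically permitted.

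**SAP 28.** State that 10MWT values kept after such an event are analysed under the assigned intervention in the planned mixed model. Record whether the participant or the assessor was unblinded after the event. Add one sensitivity analysis that leaves these values out. This gives the 10MWT data set that the present rule would have produced, so the current analysis remains available. It addresses both partial dosing and unblinding.

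Protocol 11b and SAP 13 need no change on this account.

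**Cost.** A few sentences in each document, one amendment submitted to the IRB, and at most three visits per affected participant, all already scheduled. The downside is that some kept walks may follow an incomplete round or be unblinded.

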DETAILED STUDY PROTOCOL

randomly receive each intervention block with a minimum of 2-week wash-out between blocks. We will analyze *post hoc* differences in age, impairment score, assistive device used, baseline lower extremity motor scores, and male-female ratio using independent t-tests.

- Concealment mechanism – We will conceal the intervention allocation from the evaluators performing the assessments, treatment administrators, and the study participant.
- Implementation – The PI and biostatistician will generate the allocation sequences for the cross-over study. The trial coordinator will enroll participants and study staff who are not training or assessing the participants will assign the block randomized interventions.

17. Blinding (masking)

The PI, participants, care provider, and clinical evaluators will be made aware of possible air mixtures and caffeine interventions, but not made aware of the combinatorial intervention delivered. Based upon reports from participants (N=6) blinded during our prior study,³³ 4 of 6 guessed incorrectly or were uncertain of the intervention received, suggesting our prior blinding were effective.

18. Data collection, management, and analysis

Data collection methods

- Assessment and collection plans: Physical evaluations will be completed by the study's licensed physical therapists or occupational therapists and/or trained research study staff. Functional ability of subjects will be evaluated using standard clinical assessments with high inter-rater reliability: American Spinal Injury Association Impairment Scale (AIS) lower extremity motor scores (LEMS) to quantify strength,⁵⁶ and Spinal Cord Assessment Tool for Spastic Reflexes (SCATS), and the Penn Spasm Frequency Scale (PSFS) which is a self-report assessment of the frequency and severity of muscle spasms⁵⁷ and modified Ashworth Scale to quantify spasticity.⁵⁸ We also will record pain severity using the well-established Wong-Baker FACES scale, which shows high test-retest reliability and interpretability as well as good content and construct validity.^{59, 60} Clinical ratings of walking ability, including Walking Index for Spinal Cord Injury (WISCI) II⁶¹ and/or SCI Functional Ambulation Index (SCI-FAI),⁶² will be assessed based on video recordings of the 10MWT.

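### The autonomic dysreflexia rate is divided by days in the study, which neither counts the chances for detection nor gives a separate rate for each intervention in this crossover

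*Combined protocol and SAP*

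**What the plan says.** Protocol section 18, in the paragraphs on the autonomic dysreflexia incidence rate, sets the numerator and grouping: "We will compute autonomic dysreflexia incident rate for each group as the number of autonomic dysreflexia events divided by the total person-time". The denominator follows: "We define person-time in units of person-days (the number of days a person remains in the study". The reason given is that "Person-days accounts for the total number of chances for detecting autonomic dysreflexia", together with allowance for days lost to drop-out or a disqualifying event. The relative risk is the ratio of these rates between groups.

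The same paragraphs say when an event can be found. The schedule is: "We will assess SBP at baseline, and before, during and immediately after breathing interventions, and again at follow-ups". There is one addition: "Additional SBP measurements will be made if participants first present with symptoms characteristic of autonomic dysreflexia". An event "will be diagnosed by our study team clinicians (physicians and physical therapists". Also, "An autonomic dysreflexia event will result in termination of study participation".

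Protocol section 11(a) sets 8 visits per intervention (1 baseline, 5 treatment days, 2 follow-ups) and 24 in total. On the washout, protocol section 16 and SAP section 10 say participants will "randomly receive each intervention block with a minimum of 2-week wash-out between blocks". Protocol section 13 instead words it as two weeks after the last treatment day.

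For hypertension, protocol section 18 uses person-measures, the number of blood pressure measurements taken, and gives almost the same reason about chances for detection.

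**The concern.** The reason given for person-days holds for measurements but not for calendar days. Two neighbouring safety rates share one rationale, and only the hypertension denominator satisfies it.

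The crossover adds a second difficulty. Every participant is meant to receive all three interventions, so days remaining in the study belong to the person and not to an intervention. The plan asks for a rate per group without saying how baseline, treatment and washout days are divided.

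At stake is a stated safety result. Section 18 calls it essential to learn whether these protocols provoke pathology, and names autonomic dysreflexia. With 20 participants, the choice of denominator strongly affects how large any rate looks, and this choice makes it look smaller.

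**Working it through.** The documents give no expected dysreflexia rate, event count or relative risk, so there is no figure to reproduce.

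**Inputs from the documents.** N = 20 (section 14); 8 visits per intervention (section 11(a)); break of at least 14 days (section 16).

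**Assumptions.** Two events per intervention; breaks of 14 to 56 days; baseline on the day before the first treatment. Everyone contributes a full round. This is a simplification, because an event ends participation.

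**Step 1: days without a scheduled chance of detection.** Round length = 1 baseline + 5 treatment days + w break days. The two follow-ups fall within the break. Share of days without a visit = 1 − 8/(6 + w). Rate per person-day = 2/(20 × (6 + w)). Rate per visit-day = 2/(20 × 8) = 12.5 per 1000, whatever the break.

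| Break w (days) | Round (days) | Days without a visit | Per 1000 person-days | Per 1000 visit-days |
|---|---|---|---|---|
| 14 | 20 | 60% | 5.00 | 12.5 |
| 28 | 34 | 76% | 2.94 | 12.5 |
| 56 | 62 | 87% | 1.61 | 12.5 |

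If a round is instead taken as day 0 to day 14 of Table 1 (15 days), the share is 1 − 8/15 = 47%.

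**Step 2: the literal reading.** Let T be total days in the study over all participants. The rates for A and B are e_A/T and e_B/T, so the relative risk is e_A/e_B. The breaks cancel, and so does any allowance for drop-out. Section 14 allows 17% attrition: 0.17 × 20 = 3.4, about 3 people. In the extreme case all three leave before receiving B. With 2 events in each intervention the literal relative risk is 2/2 = 1.00, whereas per round started it is (2/20)/(2/17) = 0.85. The absolute rate is diluted further. With 14-day breaks and a last round ending at day 14, a completer contributes 20 + 20 + 15 = 55 days, giving 2/(20 × 55) = 1.8 per 1000 for each intervention.

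**Step 3: days assigned by round.** With equal events, the relative risk of A to B equals B's person-days divided by A's. I took the distribution of this ratio over 20,000 simulated trials of 20 people. Each person had an independent random order, two breaks drawn evenly from whole days in the stated range, and a last round of 15 days.

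| Breaks (days) | Median | Central 95% range |
|---|---|---|
| all 14 | 1.00 | 0.91 to 1.10 |
| 14 to 28 | 1.00 | 0.81 to 1.23 |
| 14 to 56 | 1.00 | 0.70 to 1.42 |

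The spread with all breaks at 14 days comes only from which intervention happens to fall last. If last positions were balanced (7, 7 and 6 people), the totals would be 7 × 15 + 13 × 20 = 365 and 6 × 15 + 14 × 20 = 370 days, a ratio of 1.01.

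**The case against.** The strongest reply is that little turns on this. Section 10 excludes severe autonomic dysreflexia, section 11(b) excludes any history of it, and the protocol reports no adverse events in earlier five-day studies. With 20 people there may be no events, and then every denominator gives zero. The rate has no test attached, and it does not appear in the SAP text available to me. This stands as a limit on practical weight.

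Second, detection is not confined to visits, because readings prompted by symptoms are allowed. That is correct, and the 60% refers to scheduled chances only. SAP section 13 also mentions monitoring during and between interventions. The matching sentence in protocol section 11(b) refers to the 30-minute wait and the experiment, and neither describes monitoring at home.

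Third, a reader might infer that each intervention's relative risk is driven by the length of the break after it. The documents do not support that. It needs washout days to be assigned to the preceding intervention, which the plan does not say, and under the literal definition the breaks cancel. Even if days are assigned by round, randomised order and concealed allocation make the effect noise around 1. Large differences between interventions in mean round length are implausible.

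A reader might also infer that risk is understated by the ratio of round days to treatment days (20/5 = 4-fold). That would require every event to fall on a treatment day, and the plan does not claim a rate per exposure day.

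Finally, section 13 can be read as a fixed two-week washout. That would equalise the breaks, but the unobserved days and the missing assignment of days would remain.

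**Conclusion.** The concern holds in a limited form. Person-days do not count the chances for detection: about 60% of a 20-day round has no scheduled chance (47% if the round is taken as 15 days), and more with longer breaks. The definition also yields no rate specific to an intervention. The literal reading reduces the relative risk to a ratio of raw counts and defeats the stated allowance for drop-out. The by-round reading dilutes the absolute rate and adds noise to the relative risk, of the size shown above for the assumed breaks.

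The dilution of the absolute rate is systematic and does not depend on unequal breaks. No directional bias in the relative risk from break length is shown. The rates per 1000 rest on assumed event counts, and the ranges for the ratio rest on assumed breaks and an unbalanced random order. The definition should be corrected, though the consequence may be small if events are few.

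**What to change.** For each intervention, count only events and observation opportunities within that intervention's own round, from the first capsule to F2, ending at the event or withdrawal. Use visit-days attended or SBP measurements as the denominator, as already done for hypertension, and name one of them before unblinding. From the first capsule there are at most 5 + 2 = 7 visit-days, so the illustration above becomes 2/(20 × 7) = 14.3 per 1000. A rate per treatment session for on-treatment events could be added. List events with onset outside these windows separately.

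Delete the statement that person-days account for the chances for detection, and put the revised definition in the SAP. Reconcile the washout wording in protocol section 13 with protocol section 16 and SAP section 10.

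The cost is a change of wording and a recount of visits or readings already recorded, with no new procedures. The stated rate will be larger and look less favourable.
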